This study is designed as a randomized, controlled clinical study, with the first affiliated Hospital of Xi'an Jiaotong University as the research center. Participants undergoing singleton cesarean section under intraspinal anesthesia are recruited from November 1, 2021 to March 1, 2022. The diagnostic indicators of hypotension in this study are intraoperative systolic blood pressure $< 90\text{mmHg}$ or blood pressure decreased by more than 30% of basal blood pressure, the main outcome measures are the incidence of hypotension during 30 minutes after subarachnoid administration, and the secondary indicators are the specific changes of hemodynamic indexes, the usage of ephedrine, the incidence of nausea and vomiting, the incidence of dizziness, chest tightness and dyspnea during 30 minutes after subarachnoid administration, and fetal Apgar score. The patients are selected according to the inclusion and exclusion criteria, and the informed consent form are signed. First of all, the selected patients are numbered sequentially, and then the participants are randomly divided into control group and TEAS (transcutaneous acupoint electrical stimulation) group by SPSS software. In the TEAS group, 15 minutes before anesthesia at bilateral Neiguan points and Zusanli points begin to receive dense wave electrical stimulation with the frequency of 10/50Hz, and last until 30 minutes after subarachnoid administration. In the control group, 15 minutes is performed before anesthesia, and electrodes are connected at the same acupoint, but no electrical stimulation is given, the duration is the same as that of the TEAS group. During the trial, participants know which group they will be assigned to and which treatment they will receive. According to the grouping of random tables generated by SPSS, a researcher will independently give corresponding treatment measures to participants who has had signed the informed consent form, and cover up the screen of the electroacupuncture instrument. Another data collection researcher who does not know about the grouping records the vital signs and other complications of the participants. When the total number of cases reaches the minimum number of cases required by statistics or reaches the project case collection node (March 1, 2022), the data will be statistically analyzed and processed by professional statistical researchers.

Inclusion Criteria:

- 18 years \leq age < 55 years
- ASA classification I ~ II
- full term ($37\text{ weeks} \leq \text{gestational weeks} < 42\text{ weeks}$)
- schedule for elective single cesarean section under spinal anesthesia
- no other clinical trial 3 months before the enrollment
- volunteer to participate and sign the informed consent form

Exclusion Criteria:

- severe preeclampsia or hypertension
- diabetes
- cardiac insufficiency
- mental abnormality or cognitive impairment or inability to communicate
- acupuncture points skin breakage, infection, allergy
- the researchers believe that there are any conditions that are not suitable for inclusion.

Elimination Criteria:

- be unwilling to continue the trial during the trial
- have adverse reactions caused by transcutaneous acupoint electrical stimulation during the trial
- the effect of intraspinal anesthesia is not good and drugs are added or intubation is changed to general anesthesia during the trial,
- intraspinal block level is too high above T4 or too low to below T10 during the trial
- loss of blood more than 400ml during the trial

2. Research methods

In this study, a randomized, controlled design method is used to study the pregnant women who meet the inclusion criteria of singleton cesarean section.

Sample size estimation:

Based on the pre-experimental results from July 5, 2021 to July 28, 2021, the incidence of hypotension is 40% in the TEAS group and 80% in the control group. The sample size and the incidence of hypotension in the TEAS group is compared with that in the control group are estimated by GPOWER3.1 software,. Using the z test of two independent samples in the non-parametric test, double tails, $\alpha=0.05$ 、 $1-\beta=0.85$ 、 $N2/N1=1$ 、 $P1=0.40$ 、 $P2=0.80$, 26 cases in each group are calculated. A total of 52 cases. According to the 10% lost follow-up rate, the minimum sample size in each group is 29 cases, with a total of 58 cases.

Random:

Randomized grouping is obtained by using SPSS software programming. First of all, the determined sample size is numbered from small to large according to the order of the operation, and then the number is inputted into the SPSS software. The random number is generated by the random number generator in the SPSS software program, and the generated random numbers are randomly grouped.

Control:

The number,Random,group appears in the software in the running program is the patient serial number that has been arranged before, the random number generated by the software, and the grouping after randomization. 0 is defined as control group (Control group), and 1 is defined as transcutaneous acupoint electrical stimulation group (TEAS group).

Open:

The specific method of operation is that participants know which group they will be assigned

to and what kind of treatment they will receive. According to the grouping of random tables generated by SPSS, a researcher will independently give corresponding treatment measures to the participant who has had signed the informed consent form, and cover up the screen of the electroacupuncture instrument. Another data collection researcher who does not know about the grouping records the vital signs and other complications of the participant. Finally, all the data will be saved, and after all the data are collected, the professional statistical researchers will deal with the data accordingly.

Clinical intervention program

(1) group

- transcutaneous acupoint electrical stimulation group (TEAS group): 15 minutes before anesthesia, begin to receive dense wave electrical stimulation with the frequency of 10/50Hz at bilateral Neiguan and Zusanli points, and last until 30 minutes after subarachnoid administration.
- Control group (Control group): 15 minutes before anesthesia, begin to connect the electrode at the same acupoint, but no electrical stimulation is given, the duration is the same as that of the TEAS group.

(2) selection of acupoints

- Neiguan (PC6): be located on the palmar side of the forearm, two inches above the transverse carpal stria, between the tendon of the palmar longus muscle and the tendon of the radial carpal flexor muscle.
- Zusanli (ST36): be located in the anterolateral leg, three inches under the calf nose point, a transverse finger (middle finger) from the anterior tibial crest.

(3) TEAS stimulation parameters

- frequency: 10/50Hz
- waveform: dense wave
- intensity: from low to high, adjust the stimulation intensity until the patient feels slight tingling, taking the maximum inductance that the patient can tolerate, no muscle convulsions, no discomfort as the standard, and record the final stimulation intensity.
- duration: 45 minutes

3. Research steps:

Blood pressure (BP), electrocardiogram (ECG) and pulse oxygen saturation (SpO2) are measured routinely after participants included in the study entered the operating room. At the same time, the changes of cardiac function indexes such as stroke volume (SV), stroke index (SI), cardiac output (CO), cardiac index (CI), cardiac function index (CPI), systemic peripheral vascular resistance (TPR) and systemic peripheral vascular resistance index (TPRI) are monitored by impedance cardiac output measurement system. At the same time, the venous channel is established, and after the venous channel is established, the compound sodium chloride injection 10ml / kg is infused for 15 minutes to eliminate the hypotension caused by the lack of blood

volume. The blood pressure, heart rate and other hemodynamic parameters of the 5 minutes after the participants enter the room are recorded as basic values. According to the grouping situation, the participants are intervened to deal with 45 minutes. During anesthesia, the participants take the left lying position, routinely use No. 17 Tuohy needle for puncture, the puncture point is L3-4, and the No. 25 lumbar anesthesia needle is placed after reaching the epidural space. After confirming the cerebrospinal fluid outflow, the equal specific gravity local anesthetic solution is injected, the solution is 0.75% bupivacaine 2ml and cerebrospinal fluid 1ml mixture, the drug dose 2ml is injected, the injection time is 15 seconds, the lumbar anesthesia needle is pulled out, the No. 20 epidural catheter is placed, and 3-4cm is placed on the side of the head. In order to prevent the hypotension syndrome in supine position caused by uterine compression of inferior vena cava, the participants adjust the bed inclination to the left 15° ~20° immediately after supine position. The mask is given to inhale oxygen with a flow rate of 2~3L/min. The anesthesia level is determined by acupuncture along the midline of the left clavicle, and the upper limit of the sensory block plane is controlled between T6~T8 by adjusting the height of the operation bed. The other adjuvant drugs are consistent.

After subarachnoid administration, the hemodynamic data of the participants are recorded in 30 minutes every 2 minutes. When hypotension occurs, ephedrine 5-10mg is given. If the blood pressure is still low after 2 minutes, ephedrine 5-10mg can be given again until the blood pressure recovers. Atropine 0.3mg is given intravenously when bradycardia occurred.

The incidence of hypotension, nausea, vomiting, dizziness, chest tightness and dyspnea in the participants in 30 minutes after subarachnoid administration are recorded.

24 hours after operation, the satisfaction of the participants are investigated.

4. Evaluation index

Main indicators:

- the incidence of hypotension during 30mintes after subarachnoid administration

Secondary indicators:

- specific changes of hemodynamic parameters during 30minutes after subarachnoid administration
- the usage of ephedrine during 30minutes after subarachnoid administration
- the incidence of nausea and vomiting during 30minutes after subarachnoid administration
- the incidence of dizziness chest tightness and dyspnea during 30minutes after subarachnoid administration

5. Follow-up content

The satisfaction of the participants will be evaluated by follow-up 24 hours after the participants' operation.

Note:

- definition of hypotension: intraoperative systolic blood pressure < 90mmHg or blood pressure decreased by more than 30% of basal blood pressure
- definition of sinus bradycardia: heart rate < 50 beats / min

- satisfaction score: scores range from 0 to 10, the higher the score, the higher the participants' satisfaction with anesthesia

6. Technical route

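### Does ending the trial at the case target or on 1 March 2022, whichever comes first, undermine the stated 85% power?

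*Protocol*

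**What the plan says.** The opening study summary gives two triggers for closing data collection and starting the analysis: "When the total number of cases reaches the minimum number of cases required by statistics or reaches the project case collection node", the node being 1 March 2022. The same date ends the recruitment window, since participants "are recruited from November 1, 2021 to March 1, 2022". The date trigger has no minimum number attached. The protocol gives no rule for a shortfall and no expected recruitment rate.

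The target comes from the section on sample size estimation under Research methods. A pre-experiment in July 2021 supplies the assumed rates: "the incidence of hypotension is 40% in the TEAS group and 80% in the control group". With a two-sided 5% level, power 0.85 and equal allocation, "26 cases in each group are calculated", or 52 in total. The allowance for loss follows: "According to the 10% lost follow-up rate", "the minimum sample size in each group is 29 cases, with a total of 58 cases".

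**The concern.** The sample-size section describes 58 as a minimum, yet the opening summary allows analysis at any smaller number once the date arrives. The two triggers are alternatives, so nothing in the wording prevents a trial of, say, 40 women. If that happened, a non-significant result could be read against a stated power of 85% that the trial did not have.

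The case trigger is also loosely worded.

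- It refers to a number that statistics requires, and the sample-size section contains two candidates: 52 before the allowance for loss and 58 after it.
- It counts women in total, while the calculation is per group.
- It does not say whether women removed under the elimination criteria count towards the target.

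What is at stake is power and precision. Neither trigger looks at outcome data, so the false-positive rate is not in question.

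**Working it through.** **Inputs, all from the section on sample size estimation:** rates p1 = 0.40 (TEAS) and p2 = 0.80 (control); two-sided alpha 0.05 (z = 1.960); power 0.85 (z = 1.036); ratio 1:1; loss 10%. The recruitment dates come from the opening summary.

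**Step 1. Reproduce the plan's figure.** For a z test with pooled variance under the null, the mean rate is p = (0.40 + 0.80)/2 = 0.60, and

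n per group = [1.960 × √(2 × 0.60 × 0.40) + 1.036 × √(0.40 × 0.60 + 0.80 × 0.20)]² / (0.80 − 0.40)²

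= [1.960 × 0.6928 + 1.036 × 0.6325]² / 0.16 = 4.054 / 0.16 = 25.3, rounded up to 26.

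With 10% loss, 26 / 0.9 = 28.9, rounded up to 29, so 58 in total. Both figures match the protocol.

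**Step 2. Power at other totals.** With n evaluable per group,

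power = Φ[(0.40 × √n − 1.960 × 0.6928) / 0.6325],

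where n = enrolled total × 0.9 / 2. The totals 58 and 52 stand in the protocol. The others are assumptions, because it gives no accrual forecast.

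| Enrolled | Evaluable per group | Power |
|---|---|---|
| 58 | 26.1 | 86.1% |
| 56 | 25.2 | 84.8% |
| 54 | 24.3 | 83.4% |
| 52 | 23.4 | 81.9% |
| 50 | 22.5 | 80.3% |
| 40 | 18.0 | 70.4% |
| 30 | 13.5 | 57.0% |

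Among even totals, 58 is the smallest that keeps 85%, but only just: 56 falls short by 0.2 points. Losses become serious only at totals far below the plan.

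**Step 3. The accrual that is needed.** 1 November 2021 to 1 March 2022 is 120 days, or 120/7 = 17.1 weeks, and 58/17.1 = 3.4 women a week. Nothing in the protocol speaks for or against that rate at this hospital.

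**Step 4. Does counting in total matter?** Take 52 evaluable women split unequally (TEAS/control), with the pooled z test in its unequal-n form:

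| Split | Power |
|---|---|
| 21/31 | 85.1% |
| 26/26 | 85.9% |
| 29/23 | 85.3% |
| 30/22 | 84.9% |

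Every split from 21/31 to 29/23 keeps at least 85%. Exactly 26 in each group is not needed, so counting the total costs almost nothing.

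**Step 5. 52 or 58?** In the sample-size section the word minimum is attached once, to 29 per group and 58 in total. The 52 is an intermediate product. The opening summary uses the same word for its target, so 58 is the natural reading. If someone did stop at 52 enrolled, power would be 81.9% with the plan's 10% loss, about 3 points under the stated 85%.

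**The case for a change.** The best case for a change is that the protocol sets both the target and the rule that can bypass it, so this is not a gap to be left to a statistical analysis plan. The design has almost no slack, since two women fewer takes it just below 85%. Elimination is expected, because the criteria include events during surgery such as blood loss above 400 ml or a block outside the stated limits, so it matters who counts as a case. The remedy is one sentence that adds no patients beyond the planned 58.

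Part of this stands. The date trigger has no floor, and 85% holds only if about 58 women are enrolled by then. The rest is weaker.

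- The 0.85 is an input to a sample-size calculation and correct for the planned number. It does not promise what the achieved sample will deliver.
- The lowest power figures belong to totals such as 30 or 40, which the protocol does not suggest.
- The allowance for loss is already built into 58, and how eliminated women are handled in the analysis is commonly settled in the analysis plan.
- Nothing says that a short trial would be presented as having 85% power. Reporting the achieved number and a confidence interval is ordinary practice.
- Removing the end date or extending past it is not free. The protocol calls it a project node, which points to a limit on time or resources, and the document does not show that an extension is possible.

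**Conclusion.** No change follows. The stated sample size and power are correct for the plan as written, and the end date is an administrative limit that does not depend on outcomes. If the date came first, the trial would give a valid but less precise result. The cost would be about 4 points of power at 52 enrolled (86.1% to 81.9%) and about 16 points at 40 (86.1% to 70.4%). These figures assume the plan's 40% and 80% rates, 10% loss in both groups and the pooled z test. The 40 is an illustration, and the document does not show that any shortfall is likely.

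What remains is the accrual risk of any trial with a closing date, together with a target whose intended value, 58, can be read from the sample-size section. Saying so in the opening summary would be an optional clarification that alters neither the design nor the analysis.

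### The elimination criteria remove women for events after randomisation, one of which can occur only in the TEAS arm, so the hypotension comparison may not be of the randomised groups

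*Protocol*

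**What the plan says.** The protocol's Elimination Criteria form a list separate from the exclusion criteria. The first of its five items is withdrawal, worded as "be unwilling to continue the trial during the trial". The second concerns reactions to the stimulation: to "have adverse reactions caused by transcutaneous acupoint electrical stimulation during the trial". The remaining three are an inadequate block that needs supplementary drugs or conversion to a general anaesthetic, a block above T4 or below T10, and blood loss over 400 ml. The opening design summary has women selected, consented and numbered, then randomised, so all five events follow allocation.

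Three other statements bear on this:

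- **Control arm** (Clinical intervention program, (1) group): controls "begin to connect the electrode at the same acupoint, but no electrical stimulation is given".
- **Awareness of allocation** (opening design summary): "During the trial, participants know which group they will be assigned to and which treatment they will receive".
- **Outcome recording** (3. Research steps): "After subarachnoid administration, the hemodynamic data of the participants are recorded in 30 minutes every 2 minutes". The primary outcome is the incidence of hypotension in that window.

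On handling of the data, the section Open says only: "Finally, all the data will be saved, and after all the data are collected, the professional statistical researchers will deal with the data accordingly". The sample size section allows for losses: "According to the 10% lost follow-up rate, the minimum sample size in each group is 29 cases, with a total of 58 cases".

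**The concern.** A list of elimination criteria set apart from exclusion, and made up of events during the trial, reads as a rule for taking enrolled women out of the study data. Randomisation protects the comparison only if women are kept regardless of what happens after allocation. The five criteria differ in how far they threaten that.

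- **Reaction to TEAS.** A control receives no stimulation, so this criterion can remove women from one arm only.
- **Withdrawal.** Participants know their arm, so the rate and the reasons can differ between arms. Blinding the data collector prevents neither this nor the first problem.
- **Inadequate block, block level, blood loss.** These are plausibly related to blood pressure, but they bias the comparison only if they differ by arm.

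Timing adds to the problem. With readings every 2 minutes, a woman may already have met the hypotension definition before the event that eliminates her, and an observed primary outcome would then be discarded. Stimulation also starts 15 minutes before anaesthesia, so some reactions or withdrawals may come before the outcome window opens.

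With 29 women per arm, a few one-sided removals can move the estimate and, in a borderline trial, the conclusion.

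**Working it through.** **Inputs from the protocol.** Hypotension 40% (TEAS) and 80% (control); two-sided alpha 0.05; power 0.85; 1:1 allocation; 10% loss; 29 per arm.

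**Assumptions, since the protocol does not give them.** The number removed (k) and whether those removed had hypotension. I take k up to 3, because 10% of 29 is 2.9. That 10% is described as loss to follow-up, so it is only a convenient scale.

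**The plan's own figure.** Pooled z-test:

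n = [1.960·√(2·0.6·0.4) + 1.036·√(0.4·0.6 + 0.8·0.2)]² / 0.4² = 25.3, rounded up to 26.

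26 / 0.9 = 28.9, rounded up to 29. Both agree with the protocol. Power by normal approximation is 85.9% with 26 per arm and 89.6% with 29. The sample size is not in dispute.

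**Bias with no true effect.** At 80% in both arms, 29 TEAS women yield 29 × 0.8 = 23.2 expected cases. If k hypotensive TEAS women are removed, the rate among those kept is (23.2 − k)/(29 − k). The false-positive rates come from exact enumeration over Binomial(29, 0.8) in each arm with the pooled z-test.

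| k | TEAS rate kept | Bias towards TEAS | False positive favouring TEAS | Two-sided |
|---|---|---|---|---|
| 0 | 80.0% | 0 | 2.4% | 4.8% |
| 1 | 22.2/28 = 79.3% | 0.7 points | 3.0% | – |
| 2 | 21.2/27 = 78.5% | 1.5 points | 3.4% | – |
| 3 | 20.2/26 = 77.7% | 2.3 points | 4.3% | 5.9% |

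The result depends on the assumed rate. At 60% in both arms (17.4 expected cases), k = 3 gives 14.4/26 = 55.4%, a bias of 4.6 points. The false-positive rate favouring TEAS goes from 2.3% to 7.0%, and the two-sided rate from 4.6% to 8.2%.

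**Other patterns of removal.**

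- If the three TEAS women removed had no hypotension, the TEAS rate at 80% becomes 23.2/26 = 89.2%, about 9 points against TEAS.
- If those removed have the same hypotension rate as those kept, there is no bias.
- If the same share of hypotensive women (12.5%) is removed in both arms, there is no bias either.

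**Single trial results (pooled z-test), removing three hypotensive TEAS women.**

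| All randomised | After removal |
|---|---|
| 13/29 vs 23/29: 34 points, p=0.007 | 10/26 vs 23/29: 41 points, p=0.002 |
| 13/29 vs 20/29: 24 points, p=0.063 | 10/26 vs 20/29: 31 points, p=0.023 |

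Near the planned effect the conclusion stands and the estimate is exaggerated. In the borderline case the conclusion changes.

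**What an analysed result could conceal.** Suppose 10/26 vs 21/26 is reported (42 points, p=0.002) after three removals per arm. If the removed TEAS women all had hypotension and the removed controls did not, the full data were 13/29 vs 21/29 (28 points, p=0.033). In the reverse case they were 10/29 vs 24/29 (48 points, p=0.0002).

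**The case against.** The strongest reply is that the protocol gives a heading and five bullets and never says in so many words that these women are left out of the primary analysis. Elimination might mean only that treatment stops, all data are to be saved, and a statistical analysis plan that is not shown may define the analysis set. It is true that removal is a reading rather than an explicit statement, which is why the conclusion is worded as a possibility. But the alternative reading appears nowhere in the text. The objection is to a rule the protocol does state, not to an analysis set it leaves out. If only stopping treatment is meant, one sentence settles it.

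The second reply is that the effect is small. Stimulation intensity is set to avoid discomfort, and women with broken, infected or allergic skin at the acupoints are excluded, so reactions may be few. Nothing in the protocol links a reaction to hypotension, and eligibility in one arm alone creates no bias. The main illustrations assume that every removed TEAS woman was hypotensive. Part of the rise in error is also discreteness of the test: removing three TEAS women at random already gives a two-sided 5.0%, so at 80% selection adds only about 0.8 points. All of this stands and limits the weight of the point. It does not remove the structural asymmetry.

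Third, the 28-to-48-point range needs removals from the control arm, which the TEAS-reaction criterion cannot cause; the other four criteria can. Finally, readings that a withdrawing woman refuses cannot be recovered by any analysis set, and an effect under an adequate block is a legitimate secondary question. Both points are accepted in the fix.

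**Conclusion.** The concern holds. All five criteria are post-randomisation events, one can be met only in the TEAS arm, and another depends on the decision of women who know their allocation. On the natural reading, applying the list can leave a primary comparison that is not between the groups as randomised.

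The likely size is modest. With up to three selective TEAS removals and no true effect, the bias towards TEAS is 0.7 to 2.3 points at 80% hypotension, and reaches 4.6 points at an assumed 60%. The direction can reverse. These figures rest on assumed numbers removed and assumed outcomes among them. The 10% inflation of the sample size replaces lost numbers but does not correct selection. No power error is claimed: the stated 85% is met if no more than three per arm are lost.

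This should be corrected, with moderate confidence, because the protocol leaves some room over what elimination means.

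**What to change.** Replace the elimination rule, for analysis purposes, with wording to this effect:

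- The primary analysis includes all randomised women in their assigned group and uses every blood pressure reading available in the 30-minute window.
- Hypotension recorded before an elimination event counts. The 2-minute recording continues after such an event unless the woman declines.
- Every woman without a complete outcome is reported by arm and reason, including those who react or withdraw between the start of stimulation and the subarachnoid injection. A simple best-case/worst-case sensitivity analysis covers them.
- The five criteria are recorded as flags, counted by arm, and used only for a secondary per-protocol analysis.

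This concerns the analysis alone and leaves clinical management of these events unchanged.

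The cost is one paragraph of text and five flags on the record form, with no extra patients. The 2-minute schedule already exists, but the protocol should say that it continues after an elimination event. The drawback is that women with poor blocks or bleeding stay in the estimate, which may dilute it slightly. Against that, keeping all 29 per arm gives 89.6% power at 40% versus 80%, compared with 85.9% at 26 per arm.

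### The outcome recorder's masking rests only on a covered stimulator screen, while women know their group and only the TEAS arm has sensation-guided titration; the secondary symptom outcomes are mainly exposed

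*Protocol*

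**What the plan says.** The opening summary and the section headed *Open* describe the masking in nearly the same terms:

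- The trial is open for the women: "participants know which group they will be assigned" and which treatment they will get.
- One researcher delivers the allocated treatment and is to "cover up the screen of the electroacupuncture instrument".
- A second researcher is described as masked: "Another data collection researcher who does not know about the grouping records the vital signs and other complications of the participant".

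No other concealment step is described.

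Under *Clinical intervention program*, item (3), TEAS intensity is set from low to high by the woman's own sensation. Staff "adjust the stimulation intensity until the patient feels slight tingling", with the end point fixed by "taking the maximum inductance that the patient can tolerate, no muscle convulsions, no discomfort as the standard". Item (1) has staff in the control arm "begin to connect the electrode at the same acupoint, but no electrical stimulation is given". No mock titration is described. In both arms the procedure begins 15 minutes before anesthesia; in the TEAS arm stimulation is to "last until 30 minutes after subarachnoid administration", and the control duration is the same.

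Under *Research steps*, the outcomes for the same 30-minute window are listed: "The incidence of hypotension, nausea, vomiting, dizziness, chest tightness and dyspnea in the participants in 30 minutes after subarachnoid administration are recorded". Hypotension is defined in the *Note* by numeric limits on blood pressure. The symptoms have no definition and no set question wording.

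**The concern.** The second researcher is the trial's only stated protection against observer bias. A covered screen hides the display. It does not hide an exchange about sensation that takes place in one arm only, and it does not stop an informed woman from mentioning her group.

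Nausea, dizziness, chest tightness and dyspnea are sensations, so recording them depends on what the woman says and on how the recorder hears and judges it. A recorder who has learned the group could record them differently in the two arms without intending to. The report would then claim assessor masking for these outcomes on the strength of a procedure that does not secure it.

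**Working it through.** The point is one of procedure, so the main check sets the statements against the timeline.

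**Timeline from the protocol**

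| Time | Event | Recording scheduled? |
|---|---|---|
| 5 minutes after room entry | Basic values | Yes |
| 15 minutes before anesthesia | Electrodes connected in both arms; stimulation begins in TEAS only, with sensation-guided intensity | None stated |
| Subarachnoid injection | Spinal block | – |
| 0 to 30 minutes after injection | Procedure continues in both arms; hemodynamics every 2 minutes; symptoms recorded | Yes |

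The stated 45 minutes of stimulation equals 15 + 30, so it spans the whole outcome window.

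**Routes by which the recorder could learn the group**

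1. *The woman tells the recorder.* She knows her group. She is under spinal rather than general anesthesia, and the recorder notes her vital signs and complications for 30 minutes. Nothing asks her not to disclose. This route needs no assumption about where the recorder is during set-up.
2. *The titration is noticed.* It requires the woman's feedback and is specified for TEAS only. The protocol does not place the recorder at titration, and it does not keep the recorder away either.

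The covered screen closes neither route.

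**Which outcomes are exposed**

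- Hypotension (primary): a numeric threshold, read on a fixed 2-minute schedule. Little exposed.
- Nausea, dizziness, chest tightness, dyspnea (secondary): dependent on report and judgment. Exposed.
- Vomiting (secondary): can be observed, so less exposed.

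**The protocol's own figure**

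The only related number is the sample size. Inputs, from *Sample size estimation*: rates 0.40 and 0.80, two-sided alpha 0.05, power 0.85, ratio 1.

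- Pooled z formula: n = [1.960·√(2·0.60·0.40) + 1.036·√(0.40·0.60 + 0.80·0.20)]² / 0.40²
- = (1.358 + 0.655)² / 0.16 = about 25.3, so 26 per group
- With 10% loss: 26/0.9 = 28.9, so 29 per group and 58 in total

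This agrees with the protocol, and the masking point does not change it.

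**Illustration on assumed figures only**

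The protocol gives no symptom rates. Assume no true effect, 26 per group, and a two-sided 0.05 pooled z test: reject if |x₁ − x₂|/n ÷ √(2p̂(1 − p̂)/n) exceeds 1.96. Binomial probabilities are summed over all outcomes. Suppose TEAS symptoms are under-recorded by a fixed number of percentage points. The chance of a false positive is then:

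| Assumed true symptom rate | 0 points | 5 points | 10 points | 15 points |
|---|---|---|---|---|
| 20% | 5.6% | 8.3% | 18.1% | 39.9% |
| 30% | 5.5% | 7.5% | 14.1% | 26.8% |
| 40% | 5.3% | 7.1% | 12.6% | 22.4% |
| 50% | 4.5% | 6.0% | 10.7% | 19.3% |

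The table shows how sensitive a symptom comparison of this size is to differential recording from any source. It does not estimate the bias in this trial.

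**The case against.** The strongest case on the other side has four parts.

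- **Recorder's presence.** A reader might infer that titration is conducted aloud within the recorder's hearing, while the recorder is collecting data, so that every TEAS woman is identified. The protocol does not say this. It schedules recording at the basic values and again after the injection, with nothing stated in between, and it does not say how the woman conveys her sensation. The recorder may be absent. This stands: unmasking through titration is possible but not shown.
- **Primary outcome.** A reader might infer that the recorder could choose, repeat or discard readings close to 90 mmHg. No section gives the recorder that discretion. The threshold is numeric and the schedule fixed. This stands, so the point does not extend to the primary outcome in any material way.
- **Size.** One woman in an arm of 29 is 1/29 = 3.4 percentage points. That is the weight of one patient in any trial of this size and says nothing about bias. This stands.
- **Open design.** The women are unmasked by declared design, so symptoms they report themselves can be biased at source whatever the recorder knows. This also stands, and it limits what the fix can achieve. It does not answer the point, however, because the woman's open knowledge of her group is itself the most direct way for the recorder to learn it.

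The objection narrows the point. It leaves in place that the protocol claims a masked recorder and supports the claim with one measure that does not address either route.

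**Conclusion.** The recorder's masking is weakly protected and can fail, mainly for the secondary symptom outcomes. The documents do not show that it does fail. They do not support the reading that the group is disclosed to the recorder in every TEAS case, or that the hypotension result is compromised.

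The conclusion rests on two modest inferences: that a woman under spinal anesthesia can speak to the recorder during the window, and that setting intensity by her sensation needs her feedback. The size of any bias is unknown, and the table of false-positive rates rests wholly on assumed figures. The change is worth making because it costs little and concerns the masking procedure that the protocol itself states.

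**What to change.** Amend the masking text in the opening summary and in *Open*, with matching lines under *Clinical intervention program* and *Research steps*:

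1. The recorder takes the basic values, stays out of sight and hearing during electrode set-up and titration, and returns for the post-injection recordings. If the recorder must stay, the treating researcher runs the same scripted dial-up in controls with the output off. This would not mask the control women, who know their group; its only purpose is to make the two procedures look alike to the recorder.
2. Women are asked not to mention their group or their sensations from the electrodes to the recorder.
3. Symptoms are asked about with fixed wording in both arms.
4. The report states that the self-reported symptoms come from unmasked participants.

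The cost is a short amendment, a script and slight extra coordination at set-up. The treating team would have to cover monitoring while the recorder is away. No scheduled recording is lost, since none is stated between the basic values and the injection. The change reduces the recorder's share of any bias; it cannot remove the women's own reporting bias, which is why item 4 is needed.
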